5.0 Study Design and Statistical Analysis Plan

5.1 *Describe the basic study design/approach (e.g., qualitative study using five focus groups of first year students to describe assimilation into the university community; randomized controlled trial of a behavioral change intervention to increase dietary intake of whole grains; pre- post-test evaluation of new pedagogical techniques to improve adult literacy):*

Participants will be randomly assigned to experimental or control groups, stratified by demographic characteristics (e.g., drinks per day and baseline delay discounting rates). Based on our 8 years of experience recruiting this population, we expect approximately 66% retention among eligible participants. Therefore, we will enroll approximately 200 participants in order to conclude with 76 completers. We plan to enroll more than our average attrition rate because of the increased screening procedures and the time demands of the study. Randomization will be stratified on demographic characteristics (e.g., drinks per day and baseline delay discounting rate). As a result, any differences observed in our primary hypotheses will not be confounded by these variables.

EFT group participants will be asked to think about and describe the most positive event that could realistically happen at a number of delays in the future (e.g., 1 day, 2 weeks, 1 month, 1 year, 5 years, 25 years). In contrast, participants randomized to the CET condition, will be asked to think about and describe the most positive event that occurred at a number of time points from the recent past (e.g., last night from 7pm-10pm, yesterday between 4pm-7pm, yesterday between 1pm-4pm, yesterday from 10am-12pm, yesterday between 7am-10am, the night before last between 7pm-10pm, and evening before last between 4pm-7pm).

5.2 *Describe corresponding data analysis plan/approach (e.g., content analysis of focus group transcripts; descriptive analysis followed by linear regression modeling; nonparametric analysis of pre- and post-test measures):*

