14.0 Number of Subjects

14.1 Indicate the total number of subjects to be enrolled and how this number was determined (e.g., sample size calculation [show], number of available subjects in a finite pool, number of tests funding award would allow):

Although we have observed large effect sizes of EFT on DD in AUD participants in our preliminary studies (pre-post $d=1.6$; post-only $d = 0.68$), we used a more conservative medium effect size ($f= 0.25$) to inform sample sizes to increase power to detect effect on the broader range of measures proposed here (e.g., intensity of demand). Using the method proposed by Borm, Fransen, and Lemmens, and a pre- and post-measurement correlation of 0.70218, 76 total participants would be needed to complete this study (38 participants per group), assuming a type 1 error rate of 0.01 and 95% statistical power, based on an ANCOVA comparing the intervention while using the baseline measure as a fixed-effect covariate in the analysis.

We have been successfully recruiting individuals with AUD in our community for the past 8 years. Based on these 8 years of experience recruiting alcohol users into studies of comparable length and complexity, we anticipate that over 80% of consented participants will be eligible (i.e., randomized) and about 65% of those eligible individuals will complete this study. Thus, to achieve a final sample size of 76, we anticipate consenting 200 participants. We plan to enroll more than our average attrition rate because of the increased procedures and the time demands of the study.

14.2 If this is a multi-site study, indicate the number of subjects to be enrolled at this site and the total to be enrolled from all sites:

N/A

14.3 If applicable, indicate the number of potential subjects you expect to screen for enrollment, and the number of subjects you will need to complete the research procedures:

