We have developed and are currently using a separate pre-screening protocol, which occurs prior to enrolling participants into our intervention protocols, in order to effectively decrease attrition in our studies by ensuring that participants meet most inclusion/exclusion criteria (e.g., MRI scanner eligibility) prior to enrolling into the randomized study. Given that this separate screening protocol is used for all currently ongoing studies in the lab, we cannot accurately estimate the total number of potential participants we expect to screen. However, as described above, we anticipate enrolling 200 participants in order to complete a total of 76 participants. We plan to enroll more than our average attrition rate because of the increased screening procedures and the time demands of the study. Additionally the first few participants enrolled into the study may be pilots.

14.4 If the study has more than one procedure, indicate the total number of subjects to undergo each procedure separately:

All participants will undergo all sessions unless they withdraw from the study.

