Exclusion criteria include: (1) meeting moderate to severe DSM-5 criteria for substance-use disorders other than alcohol, nicotine, or marijuana, (2) having a current diagnosis of any psychotic disorder, (3) having a history of seizure disorders or traumatic brain injury, (4) having any contraindication for participation in the fMRI session, or (5) reporting current pregnancy or lactation.

Recruitment

Participants will be recruited from the community via posted flyers, word of mouth referrals, and electronic advertisements (e.g., Craigslist, Facebook). Participants may contact the lab directly via email, Facebook, phone, walk-in, face-to-face at tabling events, or completing the online pre-screening questionnaire. Participants will also be contacted directly if they have given prior permission (through previous informed consent form) or by completion of a confidential pre-screening questionnaire.

We have developed and are currently using a separate pre-screening protocol, which occurs prior to enrolling participants into our intervention protocols, to effectively decrease attrition in our studies by ensuring that participants meet most inclusion/exclusion criteria (e.g., MRI scanner eligibility) prior to enrolling into the randomized study. Given that this separate screening protocol is used for all currently on-going studies in the lab, we cannot accurately estimate the total number of potential participants we expect to screen. However, as described above, we expect enrolling 170 participants to complete 54. We plan to enroll more than our average attrition rate because of the increased screening procedures and the time demands of the study. Additionally, the first few participants enrolled into the study may be pilots.

Participant Retention

We will evaluate continuation in our study after a baseline period of drinking has been completed. We expect to retain 75% of our participants at this time point. Specifically, 75% of our participants will present with at least 4 out of 7 drinking days, and at least 4 days with 4 or more drinks or an average higher than 4 drinks per day on drinking days.

Once participants reach this study phase , we expect a 70% retention for the rest of the study.

Randomization

Participants will be randomly assigned to experimental or control groups, balanced by number of drinks per day (square root transformed) and baseline DD rates.

Sample size

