Although we have observed large effect sizes of EFT on DD in AUD participants in prior pilot studies (pre-post $d=1.6$; post-only $d = 0.68$), we used a more conservative medium effect size ($f=0.25$) to inform sample sizes and increase our power to detect effect on the broader range of measures proposed here (e.g., intensity of demand). Using a repeated measure correlation of 0.5, 52 total participants would be needed to complete this study (26 participants per group), assuming a Type I error rate of 0.01 and 80% statistical power, based on repeated measures within- between interaction ANOVA with 2 groups and 2 measurements.

Data Measures

Demographics

Demographic measures collected include age, sex, gender, ethnicity, and race.

SES

Education level, income, occupation/working status, household members

Delay discounting

To measure DD, the hyperbolic discounting model³⁸ will be fit to participants' indifference points across delays: $V=A/(1+kD)$ in which V is the immediate subjective value of the delayed option, A is its objective amount, D is its delay, and k is the only free parameter, indexing rate of discounting (larger k implies greater delay discounting, and a shorter temporal window). The discounting rate k will be log transformed to approach normality and stabilize the variance. Analysis will proceed by fitting the above equation to individual

subject data, then comparing values of discount rate $\ln(k)$ between experimental groups, as described above. We will compare fit to the hyperbolic model in comparison to alternative models as part of our third Objective.

Demand measures

To obtain dependent measures of demand, participants' data from the alcohol purchase task will be fit to a modified³⁹ exponential equation of the demand function¹⁸ to quantify the relationship between the price of alcohol and consumption: $Q=Q_0 \times 10^{k(\exp(-\alpha Q_0 C)-1)}$ where Q is consumption of the commodity, C is the price, Q_0 is the derived initial consumption without cost constraints (demand intensity), k is the span of the function in logarithmic units, and α is the demand elasticity. Values of k are set to a constant determined empirically by the actual data, leaving Q_0 and α as free parameters to be fit. Note that although the delay discounting model and the demand equations use k , they refer to different variables. Dependent measures will be compared between experimental groups, as described above.

Resting state fMRI

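### The protocol and the SAP state different sample sizes and powers (76 completers from 200 at 95%, against 52 needed and 54 expected from 170 at 80%), and neither says which governs

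*SAP*

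**What the plan says.** **Protocol.** Section 1.0 gives a sample size of 200. Section 5.1 says "we will enroll approximately 200 participants in order to conclude with 76 completers", and section 14.3 repeats both numbers. Section 14.1 derives the completer figure by the Borm ANCOVA method with f = 0.25 and "a pre- and post-measurement correlation of 0.70218", "assuming a type 1 error rate of 0.01 and 95% statistical power". Its result is "76 total participants would be needed to complete this study (38 participants per group". It adds that "to achieve a final sample size of 76, we anticipate consenting 200 participants".

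**SAP (version 1.0, 06/06/2024).** Under Sample size, "52 total participants would be needed to complete this study (26 participants per group". This rests on a within-between interaction ANOVA with f = 0.25, correlation 0.5, type I error 0.01 and 80% power. Under Recruitment, "we expect enrolling 170 participants to complete 54". That sentence refers back to an earlier description, but no earlier SAP text gives 170 or 54.

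The protocol's version log ends on 10/15/2024, four months after the SAP, and the text still carries 200 and 76. Neither document cites the other's target, says which prevails, or gives a rule for closing recruitment.

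**The concern.** Two current documents size the same trial differently in completers, enrolment, power, test and assumed correlation. A reader cannot tell how many completers the trial is meant to have or which power claim applies, and a final sample near either figure could be described as the planned one. The SAP's date follows several protocol amendments to recruitment and eligibility, so recruitment was probably under way when the smaller number appeared; the documents do not confirm this. A sample size that changes during recruitment needs a dated reason and a statement of what was known about outcomes by arm. Neither is given.

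**Working it through.** **1. SAP figure.** Noncentral F test of the group-by-time interaction, with m = 2 measurements: λ = f²·N·m/(1 − r) = 0.0625 × N × 2/0.5 = 0.25N, on 1 and N − 2 degrees of freedom, at alpha 0.01.

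| N | λ | Power |
|---|---|---|
| 50 | 12.5 | 79.9% |
| 52 | 13.0 | 81.8% |
| 54 | 13.5 | 83.7% |
| 76 | 19.0 | 95.4% |

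The smallest even N reaching 80% is 52, so the SAP's figure is reproduced. The smallest even N reaching 95% is 76, which is the protocol's figure.

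**2. Protocol figure by its own stated method.** With two equal groups, f = 0.25 is d = 0.5. Borm: n per group = 2(z₁₋α/₂ + z₁₋β)²/d² × (1 − r²). Two-sided at 0.01 with 95% power: 2 × (2.576 + 1.645)²/0.25 = 142.5; times (1 − 0.70²) = 0.51 gives 72.7, so 73 per group and **146** in total. Using 0.70218 as printed also gives 146. A one-sided test at correlation 0.70 gives 130. ANCOVA power at N = 76 (noncentral t, noncentrality 0.5 × √19/√0.51 = 3.05, 73 degrees of freedom, two-sided 0.01) is **65.8%**. So 76 does not follow from the method the protocol names.

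**3. Why the methods diverge.** They do not give f the same meaning. Write δ for the between-group difference in change, in units of the SD of a single measurement. Then λ = δ²·N/(4 × 2(1 − r)), which at r = 0.5 is δ²·N/4. Setting this equal to 0.25N gives δ = 1.0, against d = 0.5 in the ANCOVA. A power figure therefore means little unless its method is stated with it.

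**4. Do the retention rates settle the target?** SAP: 170 × 0.75 × 0.70 = 89 completers, not 54. Protocol 14.1: 200 × 0.80 × 0.65 = 104, not 76. The protocol says it is deliberately over-enrolling, but neither enrolment number leads to its completer number on the stated rates.

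**5. Conditional calculation only.** Suppose the arms were compared at 54 completers, recruitment stopped if the result was significant, and the test was otherwise repeated at 76 without adjustment. The two statistics have correlation √(54/76) = 0.843. Type I error is 1 − P(|Z₁| < c, |Z₂| < c) = 7.5% at nominal 5% (7.45% in a t-test simulation of 400,000 runs) and 1.6% at nominal 1%.

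**The case against.** A reader might infer that the trial can stop at either number and that its type I error is therefore 7.5%. The documents do not support this. No text plans a comparison of the arms at 54 or a retest at 76. If recruitment closes at either number for reasons unrelated to results, the test stays at 5%. The figures 52, 54, 170 and 200 are stated needs or expectations, not closing rules. If enrolment were what closed recruitment, the gap would be 170 against 200, and the same two-look calculation, with correlation √(170/200), would give 6.8%. Protocol 21.1 also refers monitoring to a separate Data Safety and Monitoring Plan that is not among these documents, and rules on looking at data may be there.

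A reader might also infer that the sponsor knowingly cut power from 95% to 80%. The stated powers do differ, and both totals fit one formula, but the protocol attributes 76 to another test and another correlation. Nor does the October 2024 version show a decision to keep 76: its log entry concerns a change of principal investigator, so the number may simply have been carried forward.

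These objections limit the consequence. They leave the conflict between the documents untouched.

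**Conclusion.** The point holds as an unreconciled conflict. The two documents differ by 24 completers needed (76 − 52), by 22 if the SAP's expected 54 is used, by 30 in enrolment, and by 15 percentage points in stated power. That the smaller number reflects a lower power target is a plausible inference from the shared formula, not a documented fact.

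The protocol's pairing of 76 with 95% power fails under its own stated ANCOVA (about 66%, assuming a two-sided 0.01 test, d = 0.5 and correlation 0.70), so reinstating the protocol's text would not be enough. The 7.5% belongs in a conditional note: the documents neither plan that sequence nor exclude it. It applies to one test with exactly two looks, before the multiple-testing corrections that the SAP mentions without specifying.

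**What to change.** 1. State one completer target and one enrolment number in protocol 1.0, 5.1, 14.1 and 14.3 and in the SAP under Recruitment and Sample size. Remove the 52/54 split and the back-reference that leads nowhere.
2. Beside that target, give the method, effect size, correlation, significance level and the power it delivers. Say how the 0.01 used for sizing relates to the 0.05 that SAP Statistical Principles sets for all analyses.
3. Give the date of and reason for the difference between the documents, and say whether anyone had seen outcomes by arm when it arose.
4. State that enrolment closes at the stated number regardless of results. If arms were compared before then, adjust for the looks actually taken. No standard two-look level can be assumed to fit.

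**Cost.** Wording in both documents, best done before any comparison by arm. Adopting the SAP's number, or restating power, needs no extra participants. Adopting 76 means 22 more completers than the SAP expects. At the SAP's implied yield of 54/170 (31.8%) that is about 69 more enrolled (22/0.318), or about 239 in all, which is more than the protocol's 200.

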The Alcohol Relative Reinforcement Schedule measures the extent to which alcohol serves as a reinforcer for an individual compared to other activities or substances⁴³. Participants will be asked to rate the frequency with which they engage in activities with and without alcohol and how enjoyable those activities are. Changes in alcohol reinforcing value before and after the intervention will be compared between groups (EFT and CET).

Alcohol Withdrawal Symptoms

The Alcohol Withdrawal Scale (AWSC⁴⁴) will be used to assess the severity of alcohol withdrawal symptoms. The AWS consists of a list of common withdrawal symptoms

associated with alcohol cessation, including physical and psychological manifestations. This is a 17-question where the withdrawal symptoms are scored by summing responses to a 5-point Likert scale. Severity of withdrawal symptoms will be compared between groups (EFT and CET).

Contemplation Ladder

The Contemplation Ladder is a 10-point scale that assesses readiness to change alcohol use. Changes in readiness to change alcohol before and after the intervention will be compared between groups (EFT and CET).

Penn Alcohol Craving Scale

The Penn Alcohol Craving Scale (PACS⁴⁵) is a 5-item questionnaire that measures an individual's craving to drink alcohol in the past week. Changes in alcohol craving before and after the intervention will be compared between groups (EFT and CET).

Statistical Principles

Data preparation and analysis occurs in 3 steps: (1) assessment of data integrity; (2) descriptive analyses; and (3) longitudinal analyses. To assess data integrity, the distribution of all variables will be examined, appropriate methods will be used for handling missing data, and distributional transformations will be applied if needed to meet normality assumptions. We will also evaluate data for, and report the results of, overall consistency (e.g., between self-reported use and breath sample results). A significance level of $p<0.05$ will be used for all analyses. Multiple testing corrections will be used to control for false positives. Here we present our current analysis plan for the proposed tests. We recognize that upon completion of data collection, we may identify additional hypotheses to test. We will first implement the analysis plan proposed herein, followed by additional hypotheses and analyses as secondary/explorative thereafter.

Statistical Analyses

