Objective 1: *We hypothesize that an intervention involving EFT will increase the temporal window and decrease alcohol valuation (consumption, demand, and craving).*

Our primary measure of alcohol use during the intervention period will be the daily self-reported number of drinks per day and the SOBERLINK breathalyzer screens. We will use generalized linear mixed models to compare the daily number of drinks between the EFT and CET groups. Mixed models is a method suited to the analysis of repeated measurement data. Here, the daily number of drinks will be modeled using a Poisson distribution. In the event the daily number of drinks exhibit over dispersion, other distributions, such as a negative binomial, will be considered. In a similar manner, dichotomous breathalyzer results data (positive or negative) throughout the 5-week field test will be analyzed as a function of intervention assignment, while accounting for time of day (morning, afternoon, evening) and repeated measures from each subject. Intrasubject correlation will be accounted for using an autoregressive correlation structure (AR(1)), since drinking days may be temporally related. In the event the AR(1) correlation structure is not representative of the data, other correlation structures will be considered. All missed assessments, although rare in our experience with similar field studies (approximately 5%), will be included as missing data. In the event of high rates of missing data, we will employ techniques consistent with the intention-to-treat paradigm, such as last observation carried forward methods or worst-case scenario (that all missing data is a positive BrAC measure).

Secondary analyses. In addition to the primary hypotheses listed above, we propose several additional analyses that will more fully characterize the behavior of our research participants and potentially lead to future research questions related to EFT in AUD. To this end, we hypothesize that EFT will result in changes (baseline versus post-intervention) in secondary outcome measures (e.g., Alcohol Withdrawal Symptoms Checklist). All these secondary hypotheses will be analyzed analogous to the primary hypothesis.

Covariate Plan:

We will test for individual differences in outcome measures for the intervention for each of these stratified variables. Therefore, we will include AUDIT score, SES, age, and gender in the analyses testing for an interaction between these variables and the intervention.

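### The SAP's f = 0.25 is a 1.0 SD group difference in change, so 52 completers are not powered for the conservative, medium effect that the text describes

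*SAP*

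**What the plan says.** The SAP's Sample size section reports two pilot effects of EFT on delay discounting, d = 1.6 (pre-post) and d = 0.68 (post-only). It then says "we used a more conservative medium effect size ($f=0.25$) to inform sample sizes and increase our power", naming intensity of demand as an example of the wider set of measures it has in mind. With a repeated-measures correlation of 0.5, Type I error 0.01 and 80% power, it concludes that "52 total participants would be needed to complete this study (26 participants per group". The test behind that number is a "repeated measures within- between interaction ANOVA with 2 groups and 2 measurements". Nowhere is f converted into a difference between groups.

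Statistical Principles sets a different level: "A significance level of $p<0.05$ will be used for all analyses". It adds: "Multiple testing corrections will be used to control for false positives". No method of correction is named. Under Recruitment, the SAP says "we expect enrolling 170 participants to complete 54".

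Protocol 14.1 uses the same f = 0.25 with the same description. It reaches 76 completers (38 per group) at alpha 0.01 and 95% power, for an ANCOVA with a pre-post correlation of about 0.70.

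**The concern.** The text sets f = 0.25 beside two d values and presents it as the more cautious choice. The two scales are not the same. In a 2 x 2 group-by-time interaction, f is the SD of the four cell effects divided by the single-occasion SD, and a given f stands for a much larger group difference than a reader would assume. If f = 0.25 means 1.0 SD, the plan is sized for an effect above the post-only pilot effect, not below it.

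This is the SAP's only statement of what the trial can detect, and the choice of f is justified by measures beyond delay discounting. If power for moderate effects on demand and craving is low, a non-significant result there cannot be read as evidence against such effects. A reader who relies on the present description would think that it could.

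**Working it through.** **Inputs.** From the SAP's Sample size section: f = 0.25, rho = 0.5, N = 52 (26 per group), alpha 0.01, 2 groups, m = 2 measurements, pilot d = 0.68 and 1.6. From Statistical Principles: alpha 0.05. From Recruitment: 54 completers. The outcome SD is not given, so it is set to 1 at each occasion (assumption).

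**1. Reproduce the 52.** Noncentral F with 1 and N − 2 degrees of freedom and lambda = f² × N × m/(1 − rho).

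- N = 52: lambda = 0.0625 × 52 × 2/0.5 = 13, power 81.8%.
- N = 50: power 79.9%.

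So 52 is the smallest even total that reaches 80%. Other readings do not give 52: one-sided 0.01 gives 44, alpha 0.05 gives 34, and lambda = f² × N without the factor m/(1 − rho) gives about 192. The SAP's own number therefore identifies the convention used.

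**2. Convert f to a group difference.** If the groups differ by delta SD in pre-post change, the four interaction cell effects are ±delta/4. Hence f = delta/4, and f = 0.25 gives delta = 4 × 0.25 = 1.0 SD. As a check, SD of change = √(2(1 − rho)) = 1.0 at rho 0.5, and a two-sample t test on change with 26 per group and a 1.0 SD difference also has 81.8% power. For a plain two-group comparison f = d/2, so there the same f would mean only d = 0.5.

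**3. Power of the SAP's interaction test at rho 0.5.**

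| Completers, alpha | 1.0 SD | 0.68 SD | 0.5 SD | Difference with 80% power |
|---|---|---|---|---|
| 52, 0.01 | 81.8% | 41.9% | 20.3% | 0.98 SD |
| 52, 0.05 uncorrected | 94.2% | 67.2% | 42.4% | 0.79 SD |
| 54, 0.01 | 83.7% | 43.8% | 21.3% | 0.96 SD |

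Simulation (40,000 trials per effect, 52 completers) agrees: 41.7% and 20.5% at alpha 0.01, 67.2% and 42.5% at alpha 0.05, for 0.68 and 0.5 SD.

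If the unnamed correction were Bonferroni over the five measures in protocol 5.2 (delay discounting, drinks per day, alpha, Q0, AUQ; an assumption), the level would be 0.05/5 = 0.01. The first two rows bracket these cases.

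**4. More favourable analyses, 52 completers.** Baseline-adjusted ANCOVA, residual variance 1 − rho².

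| rho, alpha | 0.68 SD | 0.5 SD |
|---|---|---|
| 0.5, 0.01 | 56% | 29% |
| 0.70, 0.01 | 77% | 45% |
| 0.5, 0.05 | 79% | 53% |
| 0.70, 0.05 | 92% | 70% |

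Power for 0.5 SD stays below 80% throughout.

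**5. Protocol 14.1.** With 38 per group, alpha 0.01 and correlation about 0.70, the named ANCOVA at d = 0.5 has 66% power. Reaching 95% would need 74 to 75 per group (148 to 150 in total). At 38 per group, 95% power is reached at d of about 0.71. The SAP's interaction formula with rho 0.5 gives 95.4% at N = 76 and 94.8% at N = 74, so 76 coincides with that calculation. The protocol does not say which effect, in SD units, it means.

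**The case against.** The arithmetic is not disputed; the case on the other side concerns what it shows.

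- **Nothing is miscalculated, and medium is attached to f, not to d.** This is true of the 52. The sentence nevertheless claims caution relative to pilot effects quoted as d, and on that scale the target is 1.0.
- **1.0 SD is below the pre-post d of 1.6.** This stands. However, the documents do not say that 1.6 is a between-group effect. In randomised groups with equal baselines, the difference in change equals the post-only difference, so 0.68 is the relevant comparison. If 1.6 were the same effect scaled by the SD of change, then √(2(1 − rho)) = 0.68/1.6 = 0.425, or rho of about 0.91, against the 0.5 and 0.70 that the documents assume.
- **The trial may finish with more than 52.** The protocol plans 76, and the SAP's own retention rates give 170 × 0.75 × 0.70 = 89, not 54. At 0.68 SD and alpha 0.01, 76 completers give 63% (change score, rho 0.5) to 93% (ANCOVA, rho 0.70), and 88 give 71% to 96%. These figures are right and show that the final sensitivity is unsettled. They do not alter what the SAP says 52 completers deliver.
- **The source of the protocol's 76 is inferred.** This stands: the match with the interaction formula is a coincidence of numbers, not something the protocol states. The 66% applies to d = 0.5, which is what f = 0.25 means for two groups.
- **The planned models use more than two time points.** These powers describe the test that the SAP used for sizing, and a mixed model could differ.
- **The SAP says nothing about how to interpret null results.** This is correct; the risk lies in how a reader would use the description.

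**Conclusion.** The concern holds. The sample size of 52 is correct for its formula, but the effect it targets is misdescribed. For continuous pre/post outcomes (ln(k), demand, craving), 52 completers have 80% power at alpha 0.01 only for a group difference in change of about 1.0 SD (0.98 SD at exactly 80%). At the SAP's own post-only pilot effect of 0.68 SD power is 42%. At 0.5 SD it is 20%, so such an effect would be missed about four times in five. At uncorrected p<0.05 the figures are 67% and 42%.

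This rests on the interaction convention recovered from the SAP's own number, rho = 0.5, equal baselines for the comparison with 0.68, and 52 completers. Higher correlation, baseline adjustment or more completers raise the power. The conclusion does not extend to daily drinks, for which the SAP says "the daily number of drinks will be modeled using a Poisson distribution", with a negative binomial as a possible alternative, nor to breathalyzer results. Protocol 14.1 shares the undefined f, and its 95% does not hold for the ANCOVA it names at d = 0.5.

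**What to change.** In the SAP's Sample size section, delete the description of f = 0.25 as conservative and medium, and state along these lines:

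> For continuous pre/post outcomes, 52 completers give 80% power at alpha 0.01 (pre-post correlation 0.5) to detect a between-group difference in change of about 1.0 SD; power is about 42% for 0.68 SD and 20% for 0.5 SD. At p<0.05 before multiplicity correction, the detectable difference is 0.79 SD and power is 67% and 42%.

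Give the figures at the alpha and completer number actually adopted. If a baseline-adjusted analysis is chosen, state its power instead (for 0.68 and 0.5 SD at alpha 0.01: 56% and 29% at rho 0.5; 77% and 45% at rho 0.70).

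In protocol 14.1, define f in SD units and state the power of the named ANCOVA for that effect.

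The cost is wording in two paragraphs and a less favourable statement of sensitivity. No participants are added and no analysis changes.
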